## 2.4 Rationale

CXCR4 is expressed on WM cells (Ngo et al, 2008, Rocarro et al, 2014) and dysregulation of CXCR4 path signaling is common in WM (Hunter et al, 2016). Up to 40% of WM patients harbor a somatic activating mutation that supports tumor growth and survival, as well as drug resistance against many agents used to treat WM in response to its ligand CXCL12 (Hunter et al, 2014; Cao et al, 2014; Rocarro et al, 2014; Cao et al, 2015). CXCR4 mutations are almost always expressed in WM patients with mutated MYD88, and are associated with loss of genes that regulate MYD88 signaling (Hunter et al, 2016). Gene overexpression of CXCL12 has also been observed in WM cells regardless of CXCR4 mutation status, and contributes to enhanced CXCR4 signaling (Hunter et al, 2016). The use of CXCR4 antagonists may therefore offer a targeted approach to therapy of WM patients with WHIM-like somatic mutations. It is thus hypothesized that ulocuplumab will improve overall and major responses, and response kinetics to ibrutinib in symptomatic patients with CXCR4 mutated WM.

## 2.5 Correlative Studies Background

In most WM patients, CXCR4 mutations are subclonal with an estimated median cancer cell fraction of 40-50%, though the transcriptional signature remains relatively homogeneous despite the subclonal nature of CXCR4 mutations in WM (Hunter et al, 2016; Xu et al, 2016). CXCR4 mutated patients also show loss of regulatory genes that regulate MYD88 signaling (Hunter et al, 2016). Furthermore, the presence of CXCR4 WHIM mutations confers enhanced activation of AKT and ERK (Cao et al, 2014; Cao et al, 2015). Bone marrow aspirate (approximately 45cc) will therefore be collected at the baseline screening visit, on day 1 of cycle 2 (phase 1 participants only), at the completion of cycle 6 following the last ulocuplumab infusion, at year 1, and thereafter every year until study completion. Bone marrow lymphoplasmacytic cells will be genotyped for MYD88 and CXCR4 at baseline to determine eligibility, and at every BM sampling for the cancer cell fraction of mutated CXCR4 cells determined by next generation (whole exome) sequencing; ii) wild-type and mutated CXCR4 transcriptional signature determined by transcriptome analysis; and iii) CXCR4, CXCR7 cell surface expression, pAKT, and pERK determined by multicolor flow cytometry.

### 3. PARTICIPANT SELECTION

#### 3.1 Eligibility Criteria

Participants must meet the following criteria on screening examination to be eligible to participate in the study:

- 3.1.1 Clinicopathological diagnosis of Waldenstrom's Macroglobulinemia and meeting criteria for treatment using consensus panel criteria from the Second International Workshop on Waldenstrom's macroglobulinemia (Kyle et al, 2003) or have high risk disease with an serum IgM level of 6,000 mg or higher (Gustine et al, 2016).
- 3.1.2 MYD88 and CXCR4 mutated disease (determined by [name] laboratory or molecular diagnostics laboratory).
- 3.1.3 Measurable disease, defined as presence of serum immunoglobulin M (IgM) with a minimum IgM level of >2 times the upper limit of normal of each institution is required.
- 3.1.4 Age  $\geq$  18 years
- 3.1.5 ECOG performance status  $\leq 2$  (see Appendix A.).
- 3.1.6 To establish eligibility, participants must have adequate organ and marrow function as defined below:
  - Absolute neutrophil count  $\geq 1,000/\mu\text{L}$  independent of growth factor support within 7 days of screening
  - Platelets  $\geq 75,000/\mu\text{L}$  independent of platelet transfusions within 7 days of screening
  - Hemoglobin  $\geq 8 \text{ g/dL}$
  - Total bilirubin  $\leq 1.5 \text{ mg/dL}$  or  $< 2 \text{ mg/dL}$  if attributable to hepatic infiltration by neoplastic disease or Gilbert's syndrome
  - AST(SGOT)/ALT(SGPT)  $\leq 2.5 \times$  institutional upper limit of normal
  - Creatinine  $\leq 2 \text{ mg/dL}$
- 3.1.7 Not on any active therapy for other malignancies with the exception of topical therapies for basal cell or squamous cell cancers of the skin.
- 3.1.8 Females of childbearing potential (FCBP) must agree to use two reliable forms of contraception simultaneously or have or will have complete abstinence from heterosexual intercourse during the following time periods related to this study: 1) while participating in the study; and 2) for at least 28 days after discontinuation from the study. Men must agree to use a latex condom during sexual contact with a FCBP even if they have had a successful vasectomy. FCBP must be referred to a qualified provider of contraceptive methods if needed. FCBP must have a negative serum pregnancy test at screening.
- 3.1.9 Able to adhere to the study visit schedule and other protocol requirements.

3.1.10 Ability to understand and the willingness to sign a written informed consent document.

### **3.2 Exclusion Criteria**

Participants who exhibit any of the following conditions at screening will not be eligible for admission into the study.

- 3.2.1 Any serious medical condition, laboratory abnormality, uncontrolled intercurrent illness, or psychiatric illness/social condition that would prevent study participation.
- 3.2.2 Concurrent use of any other anti-cancer agents or treatments or any other investigational agents.
- 3.2.3 Treatment with strong CYP3A4/5 inhibitors or inducers
- 3.2.4 Prior exposure to ibrutinib or ulocuplumab
- 3.2.5 With the exception of low-dose aspirin, subjects enrolled in this study should not take concomitant medications that durably inhibit platelet function including marine oil tablets. For such medications a wash-out period of  $\geq$  7 days is required prior to starting treatment. Agents which inhibit platelet function transiently or inhibit coagulation by other mechanisms are restricted (e.g. use with caution). Medications that directly and durably inhibit platelet function include aspirin containing combinations, clopidogrel, dipyridamole, tirofiban, epoprostenol, eptifibatide, cilostazol, abciximab, ticlopidine, cilostazol.
- 3.2.6 Participants should not take drugs that directly and durably inhibit coagulation with the exception of warfarin (coumadin) and heparin including low-molecular-weight heparin (LMWH), including enoxaparin, tinzaparin, etc.
- 3.2.7 Participants enrolled in this study should not take concomitant medications that are considered to have a risk of Torsades de Pointes (category 1 on <http://www.qtdrugs.org/medical-pros/drug-lists/drug-lists>). For such medications a wash-out period of  $>7$  days is required prior to starting treatment.
- 3.2.8 Any condition, including the presence of laboratory abnormalities, which places the participant at unacceptable risk if he/she were to participate in the study or confounds the ability to interpret data from the study.
- 3.2.9 Known CNS lymphoma.
- 3.2.10 New York Heart Association classification III or IV heart failure.
- 3.2.11 Known history of Human Immunodeficiency Virus (HIV), active infection with Hepatitis B Virus (HBV), and/or Hepatitis C Virus (HCV).

3.2.12 Lactating or pregnant women.

3.2.13 Grade > 2 toxicity (other than alopecia) continuing from prior anti-cancer therapy.

3.2.14 Inability to swallow capsules

3.2.15 History of non-compliance to medical regimens.

### **3.3 Inclusion of Women and Minorities**

Both men and women of all races and ethnic groups are eligible for this trial.

## **4. REGISTRATION PROCEDURES**

### **4.1 General Guidelines for DF/HCC Institutions**

Institutions will register eligible participants in the Clinical Trials Management System (CTMS) OnCore. Registrations must occur prior to the initiation of protocol therapy. Any participant not registered to the protocol before protocol therapy begins will be considered ineligible and registration will be denied.

An investigator will confirm eligibility criteria and a member of the study team will complete the protocol-specific eligibility checklist.

Following registration, participants may begin protocol therapy. Issues that would cause treatment delays should be discussed with the Overall Principal Investigator (PI). If a participant does not receive protocol therapy following registration, the participant's registration on the study must be canceled. Registration cancellations must be made in OnCore as soon as possible.

### **4.2 Registration Process for DF/HCC Institutions**

DF/HCC Standard Operating Procedure for Human Subject Research Titled *Subject Protocol Registration* (SOP #: REGIST-101) must be followed.

### **4.3 General Guidelines for Other Investigative Sites**

N/a

### **4.4 Registration Process for Other Investigative Sites**

N/a.

## **5. TREATMENT PLAN**

Treatment will be administered on an outpatient basis. No investigational or commercial agents or therapies other than those described below may be administered with the intent to treat the participant's malignancy.

## 5.1 Treatment Regimen

Treatment will be administered in four-week cycles. Treatment will be comprised of ibrutinib administered orally starting day 1 of cycle 1 for 47 cycles, along with ulocuplumab administered intravenously weekly during Cycle 1, and then every other week for Cycles 2-6. A 3+3 Phase I design will be employed for 3 dose levels, and 20 additional patients will be recruited at the maximum dose or maximum tolerated dose (if a dose-limiting toxicity is identified) for the Phase II dose expansion.

Bristol-Myers Squibb, the study supporter and manufacturer of ulocuplumab, terminated the development of ulocuplumab on 3/29/19. Due to this, the Phase 2 portion of this study was never opened. BMS continued to supply drug for this study until 7/1/2020. The Sponsor-Investigator halted enrollment on this study after the 3rd participant in the Phase 1 cohort #3 was accrued. All participants enrolled were able to complete planned ulocuplumab dosing, and participants then continued on commercial ibrutinib monotherapy.

The Sponsor-Investigator has decided to discontinue all study therapy and follow-up procedures for all participants remaining on the study as of 12/31/22.

Each cycle is four weeks. Ibrutinib will be administered continuously for 47 cycles. Ulocuplumab will be administered weekly on days 1, 8, 15, and 22 ( $\pm$  2 days for each dose) for Cycle 1, then every other week on days 1 and 15 ( $\pm$  2 days) for Cycles 2-6. For the Phase I portion, a 3+3 design will be used following the dosing schema in Table 1.

**Table 1. Cohort dosing**

Dose Level	Ibrutinib	Ulocuplumab Cycle 1	Ulocuplumab Cycles 2-6
Cohort 1 –Starting dose	420mg PO DQ	400 mg weekly	800 mg every other week
Cohort 2	420mg PO DQ	800 mg weekly	1200 mg every other week
Cohort 3	420mg PO DQ	800 mg weekly	1600 mg every other week

The MTD or highest administered dose informed from the Phase I portion of the study will be used in Phase II portion of the study.

Participants will be pre-medicated with 10mg of oral dexamethasone and 20mg of oral famotidine (or equivalent for either agent) 8-18 hours prior to each dose of ulocuplumab, in addition to 30-60 minutes before each treatment.

Regimen Description					
Agent l	Premedications; Precautions 30-60 minutes before ulocuplumab infusion	Dose	Route	Schedule	Cycle Length

Ulocuplumab	1. Diphenhydramine 25-50 mg IV or PO 2. Acetaminophen 650 mg orally 3. Corticosteroids (10 mg of IV dexamethasone or equivalent) 4. Famotidine (or equivalent) 20 mg PO or IV*	Refer to Table 1. Cohort Dosing	IV	Cycle: 1 Days 1, 8, 15, and 22 ± 2 days Cycles 2-6: Days 1 and 15 ± 2 days	28 days (4 weeks)
Ibrutinib	Not applicable	420mg	PO	QD (outpatient)	28 days (4 weeks)

 The order of administration of Ibrutinib and Ulocuplumab does not matter.

\*Oral famotidine or equivalent may be given in the event of drug shortages or formulary changes.

Reported adverse events and potential risks are described in Section 7. Dose modifications are described in Section 6. No investigational or commercial agents or therapies other than those described below may be administered with the intent to treat the participant's malignancy.

## 5.2 Pre-Treatment Criteria

C1D1 results do not need to meet eligibility parameters. Day 1 chemistry and hematology laboratories must be reviewed prior to treatment.

Participants must meet the following criteria on Day 1 of all cycles:

- No grade 3 or 4 nausea, vomiting, or diarrhea (if persistent despite optimal antiemetic and/or antidiarrheal therapy)
- No non-hematologic grade 3 toxicities
- Neutrophil count  $\geq$  750/uL (growth factor permitted to retreat)
- Platelet count  $\geq$  50,000 uL (platelet transfusion permitted to retreat)
- Hemoglobin  $\geq$  8 g/dL

## 5.3 Treatment Administration

### 5.3.1 Ulocuplumab

Ulocuplumab (400mg, 800mg, 1200mg, or 1600mg flat dose) will be administered as a single 60 minute intravenous infusion. Participants should be observed for one hour after the completion of every infusion.

Ulocuplumab will be administered 30-60 minutes after pre-medications on Day 1, 8, 15, and 22 of Cycle 1 ( $\pm$  2 days for each dose), and Days 1 and 15 for Cycles 2-6 ( $\pm$  2 days for each dose).

Vital signs (blood pressure, temperature, heart rate, respiratory rate) will be obtained before infusion, every 15 minutes ( $\pm$  5 minutes) during the infusion period, and at 15, 30, and 60 minutes ( $\pm$  5 minutes) after the completion of infusion.

Since ulocuplumab contains only human protein sequences, it is unlikely to be immunogenic and to induce infusion or hypersensitivity reactions. However, if such a reaction were to occur, it

might manifest with fever, chills, rigors, headache, rash, pruritis, arthralgias, hypo or hypertension, bronchospasm, or other symptoms.

For Grade 1 symptoms, i.e. mild reaction for which infusion interruption is not indicated, and intervention is not indicated:

Patient will remain at the clinic and monitored until there is recovery from symptoms. Continuation of infusion as before can proceed until infusion is completed. Information on prophylactic pre-medications is provided in Section 5.7.1.

For Grade 2 symptoms, i.e. moderate reaction that requires infusion interruption, and that necessitates intervention such as antihistamines, non-steroidal, or anti-inflammatory agents (NSAIDs), narcotics, corticosteroids, or intravenous fluids. Patients will remain at the clinic and monitored until there is recovery from symptoms. Infusion may be restarted at 50% of the original infusion rate when symptoms resolve. If no further complications occur after 30 minutes, the rate may be increased to 100% of the original infusion rate. Subject should be monitor closely at this time. If symptoms recur, then the infusion will be stopped and no further ulocuplumab will be administered at that visit. The amount of study drug infused must be recorded on the case report form (CRF). Patient will be monitored until recovery from symptoms.

For prolonged Grade 3 or Grade 4 symptoms, i.e. severe reactions that are severe or not rapidly responsive to symptomatic medication and/or interruption of infusion, or recurrence of symptoms following initial improvement, study drug should be terminated. An intravenous infusion of normal saline, and support as follows can be considered by the treating clinician: bronchodilators, epinephrine 0.2 to 1 mg of a 1:1,000 solution for subcutaneous administration, 0.3 mg of a 1:1,000 solution for intramuscular administration, or 0.1 to 0.25 mg of a 1:10,000 solution injected slowly for i.v. administration, and/or diphenhydramine 50 mg i.v. with methylprednisolone 100 mg i.v. (or equivalent), as needed. The subject should be monitored until the treating clinician is comfortable that symptoms will not recur. Ulocuplumab will be permanently discontinued. Investigators should follow their institutional guidelines for the treatment of anaphylaxis, and treating clinician should if possible remain at bedside and monitor the subject until recovery from symptoms.

In the case of late occurring hypersensitivity symptoms (e.g., appearance of a localized or generalized pruritus within 1 week after treatment), symptomatic treatment may be given (e.g., oral antihistamine, or corticosteroids).

Product description and storage information is described in Section 8.

### **5.3.2 Ibrutinib Administration**

Ibrutinib 420 mg will be prescribed per the FDA package label, administered orally once daily for 47 cycles. The capsules should be taken around the same time each day with 8 ounces (approximately 240 mL) of water. The capsules should be swallowed intact and subjects should not attempt to open capsules or dissolve them in water. The use of strong CYP3A inhibitors/inducers, and grapefruit and Seville oranges should be avoided for the duration of the

study (see section 5.7.3).

If a dose of ibrutinib is not taken at the scheduled time, it can be taken as soon as possible within 6 hours, with a return to the normal schedule the following day. The subject should not take extra capsules to make up the missed dose.

Participants will be treated with ibrutinib for 47 cycles or until progression, unacceptable toxicity, or decision to withdraw from the trial. Dose reductions due to toxicity will be permitted on information seen in Section 6.

Ibrutinib will be self-administered, and participants will be instructed to write in a diary daily, documenting that the drug was taken. Participants will be instructed to take the study drug at approximately the same time each day, ideally at least 30 minutes before eating or at least 2 hours after a low-fat meal. Participants will also be instructed on how to complete the diary. Participants will be reminded that dietary habits around the time of ibrutinib intake should be as consistent as possible throughout the study. If a dose is missed, study drug may be taken up to 6 hours after the scheduled time with a return to the normal schedule the following day. If it has been greater than 6 hours, ibrutinib should not be taken on that date, and the patient should take the next ibrutinib dose at the scheduled time the next day. The missed dose will not be made up and must be returned at the next scheduled visit. The patient will be instructed to document missed drug doses in the study diary. Furthermore, they will be instructed to call the PI or research nurse if vomiting occurs. If the pills are vomited, this should be noted on the patient diary, but a replacement dose should not be taken that day. All dosages prescribed and dispensed to the participant, and all dose changes during the study must be recorded.

$\leq 1$ out of 6 at highest dose level below the maximally administered dose	This is generally the recommended phase 2 dose.

## 5.5 Definition of Maximum Tolerated Dose (MTD) for Ulocuplumab (from Phase I)

The MTD is defined as the highest combination drug dosage not causing medically unacceptable, dose-limiting toxicity (DLT) in more than 33% of the treated participants in the first cycle and second cycle of treatment. Adverse events and laboratory abnormalities that are considered DLTs are defined in Section 5.4. The MTD or maximum dose from Phase I portion of the study will be used in the phase II part of the study.

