(DLT) is observed after cycle 1 & 2 in any of these subjects, the trial will proceed to enroll additional subjects into the next higher dose cohort. If one subject develops a DLT at a specific dose, an additional three subjects will be enrolled into that same dose cohort. Development of DLTs in more than 1 of 6 subjects in a specific dose cohort will be deemed that the MTD has been exceeded, and further dose escalation will not be pursued. All patients will receive ibrutinib at 420 mg orally per day beginning day 1 of cycle 1 for 47 cycles.

Ulocuplumab will be administered on day 1  $\pm$  2 days weekly for cycle 1 (Days 1, 8, 15, 22), then day 1  $\pm$  2 and day 15  $\pm$  2 for cycles 2-6. Participants will be evaluated for tolerance and response on the first day they receive treatment for each cycle beginning with cycle 2, at the end of treatment which will occur 4 weeks  $\pm$  1 week after the last administered therapy, and every 12 weeks  $\pm$  1 week thereafter as long as the participant remains on study. Participants will be eligible to continue therapy and remain on study so long as they do not have unacceptable toxicity or demonstrate progressive disease.

Response criteria updated at the Sixth International Workshop on Waldenström's macroglobulinemia (Owen et al, BJH 2013) will be used to assess response, stable disease, and progressive disease.

Bristol-Myers Squibb, the study supporter and manufacturer of ulocuplumab, terminated the development of ulocuplumab on 3/29/19. Due to this, the Phase 2 portion of this study was never opened. BMS continued to supply drug for this study until 7/1/2020. The Sponsor-Investigator halted enrollment on this study after the 3rd participant in the Phase 1 cohort #3 was accrued. All participants enrolled were able to complete planned ulocuplumab dosing, and participants then continued on commercial ibrutinib monotherapy.

The Sponsor-Investigator has decided to discontinue all study therapy and follow-up procedures for all participants remaining on the study as of 12/31/22.

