## CYP3A- Inhibitors/Inducers

Ibrutinib is metabolized primarily by CYP3A. Avoid co-administration with strong CYP3A4 or moderate CYP3A inhibitors and consider alternative agents with less CYP3A inhibition.

- If a strong CYP3A inhibitor (eg, ketoconazole, indinavir, nelfinavir, ritonavir, saquinavir, clarithromycin, telithromycin, itraconazole, nefazadone, or cobicistat) must be used, withhold ibrutinib treatment for the duration of inhibitor use.
- If a moderate CYP3A inhibitor (eg, voriconazole, erythromycin, amprenavir, aprepitant, atazanavir, ciprofloxacin, crizotinib, darunavir/ritonavir, diltiazem, fluconazole, fosamprenavir, imatinib, verapamil, amiodarone, or dronedarone) must be used, reduce ibrutinib to 140 mg PO QD for the duration of the inhibitor use. Avoid grapefruit and Seville oranges during ibrutinib/placebo treatment, as these contain moderate inhibitors of CYP3A.
- No dose adjustment is required in combination with mild inhibitors.

Avoid concomitant use of strong CYP3A inducers (eg, carbamazepine, rifampin, phenytoin, and St. John's Wort). Consider alternative agents with less CYP3A induction.

No chronic treatment with systemic steroids (at dosages equivalent to prednisone > 20 mg/day for more than 14 days) or other immunosuppressive agents should be used. Topical or inhaled corticosteroids are allowed.

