## 11. MEASUREMENT OF EFFECT

### 11.1.1 Definitions

**Evaluable for toxicity:** All participants who receive at least one dose of study treatment will be evaluable for toxicity from the time of their first treatment.

**Evaluable for objective response:** Only those participants who have measurable disease present at baseline, have received at least one cycle of therapy, and have had their disease re-evaluated will be considered evaluable for response. These participants will have their response classified according to the definitions stated below. (Note: Participants who exhibit objective disease progression or die prior to the end of cycle 1 will also be considered evaluable.)

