## 13.2 Sample Size, Accrual Rate and Study Duration

A maximum of 18 patients will be accrued for the phase I study.

A maximum of 20 evaluable patients will be accrued for the phase II study. To be evaluable for response, patients must have one cycle of therapy. Patients inevaluable for response will be replaced. Assuming an H0 of major response rate of 50% vs. an H1 of 80%, a sample of 20 patients would have a power of 80% with an alpha of 0.04 to detect a difference. If 15 patients or more obtain a major response, then the study would be a success, if 14 patients or fewer obtain a major response, then the study would be a failure and the combination should not continue further evaluation. Sample size and power estimation were obtained using the binomial method (STATA version 13).

Accrual time will be approximately 12-18 months, at a rate of 2-3 patients per month. Patients will be followed for the duration of time on active protocol therapy (47 cycles), and then 2 additional years after completion of cycle 47. Participants will be followed for up to 24 months after completion of protocol therapy, or until termination from study, disease progression, initiation of new anti-neoplastic therapy, or death. Participants removed from protocol therapy for unacceptable adverse event(s) will be followed until resolution of the adverse event to at least grade 1 or less, or stabilization of the adverse event.

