## **13.7 Reporting and Exclusions**

### **13.7.1 Evaluation of Toxicity**

All participants who receive at least one dose of any test material during the study will be included in the safety analysis.

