### **13.7.2 Evaluation of the Primary Efficacy Endpoint**

All participants who have received at least one cycle of therapy are eligible for response assessment. Inevaluable patients for response will be replaced. All conclusions will be based on evaluable participants.

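### The Phase I 3+3 has no DLT-evaluable definition or replacement rule, so read literally a participant lost in Cycles 1-2 without a DLT counts as a DLT-free place (minor)

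*Combined protocol and SAP*

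**What the plan says.** The Phase I objective (1.2) is the dose of ulocuplumab that can be given with ibrutinib. The escalation tables in 5.4 and 13.1 count DLTs out of 3 or 6 participants over Cycles 1 and 2. Section 5.5 sets the MTD limit as DLT "in more than 33% of the treated participants in the first cycle and second cycle of treatment".

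Three other parts of the plan bear on who counts:

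- **Toxicity evaluability.** Section 11.1.1: "All participants who receive at least one dose of study treatment will be evaluable for toxicity from the time of their first treatment". Section 13.7.1: "All participants who receive at least one dose of any test material during the study will be included in the safety analysis". Both are general safety definitions. No other is given for the 3+3.
- **Replacement.** Section 13.7.2: "Inevaluable patients for response will be replaced". Section 13.2 says the same for Phase II. Neither covers participants inevaluable for DLT.
- **Timing.** Section 1.1 escalates if no DLT "is observed after cycle 1 & 2 in any of these subjects, the trial will proceed to enroll additional subjects" at the next level.

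On Phase I size, 13.2 says: "A maximum of 18 patients will be accrued for the phase I study". On conduct, 1.1 reports: "All participants enrolled were able to complete planned ulocuplumab dosing, and participants then continued on commercial ibrutinib monotherapy".

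**The concern.** Each 3+3 decision rests on three or six people, so one person is a third or a sixth of the evidence on a level. The plan defines evaluability and replacement for response but not for the endpoint that decides the dose.

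Two routes out of the window need no DLT. A participant may choose to withdraw (5.8). Or, under the CYP3A rules in 5.7.3, if a strong inhibitor "must be used, withhold ibrutinib treatment for the duration of inhibitor use", the participant is off one of the two drugs. The second route is narrow: strong inhibitors are barred at entry (3.2.3) and new medications need prior consultation (5.7).

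If such a person is counted as free of DLT, and less exposure does not raise DLT risk, the level looks safer than it is. Interruptions for study-drug toxicity are a separate matter: many are DLTs, and the rest belong in the count.

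**Working it through.** **The plan's own figure.** Three dose levels at up to six each gives 3 × 6 = 18, which matches the 13.2 maximum. It has no allowance for replacements if all three levels expand to six.

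**Inputs.** From 5.4 and 13.1: 0 of 3 escalates; 1 of 3 adds three more, and 0 of those 3 escalates; anything else stops. Assumed, because the documents give neither: a true two-cycle DLT probability p of 0.30, 0.40 or 0.50, and a proportion q of 5% or 10% lost without a DLT.

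**Chance that a level passes, nobody lost.** Pass(p) = (1−p)³ + 3p(1−p)² × (1−p)³. At p = 0.40: 0.216 + 0.432 × 0.216 = 0.309.

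**Loss averaged over cohorts, no risk time for those lost (upper end).** The counted rate becomes p′ = p(1−q). At p = 0.40 and q = 0.10, p′ = 0.36 and Pass = 0.2621 + 0.4424 × 0.2621 = 0.378.

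**Loss averaged over cohorts, exit midway at constant hazard.** p′ = p(1−q) + q(1−√(1−p)). At p = 0.40 and q = 0.10, p′ = 0.36 + 0.10 × 0.2254 = 0.3825 and Pass = 0.338.

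**One of the first three lost at once, later three complete.** (1−p)² + 2p(1−p) × (1−p)³. At p = 0.40: 0.36 + 0.48 × 0.216 = 0.464.

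| Probability of passing the level | p = 0.30 | p = 0.40 | p = 0.50 |
|---|---|---|---|
| Nobody lost | 0.494 | 0.309 | 0.172 |
| 5% lost, midway | 0.508 | 0.324 | 0.184 |
| 10% lost, midway | 0.523 | 0.338 | 0.196 |
| 5% lost, no risk time | 0.525 | 0.343 | 0.202 |
| 10% lost, no risk time | 0.557 | 0.378 | 0.234 |
| One of first three lost at once | 0.634 | 0.464 | 0.312 |

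Against the first row, midway exit adds about 1 to 3 percentage points, no risk time about 3 to 7, and one immediate loss about 14 to 15. The last row is conditional on that loss. The chance that at least one of three is lost is 1 − 0.95³ = 14% at 5%, or 1 − 0.90³ = 27% at 10%.

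**The case against.** **The plan is silent; it does not state that dropouts count.** This is partly right. No sentence says how an early leaver is handled. The wording in 1.1 presupposes that all three are observed through Cycle 2, and 5.5 could be read as meaning people treated in both cycles. But neither sets a minimum exposure to either drug or says what happens when someone falls short. The only toxicity-evaluability definitions available require one dose.

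**The DSMC would see it.** Section 12.2 says the information supplied may include dose-level and DLT data, so there is oversight during Phase I. It supplies no denominator rule. The dedicated review in 5.6 follows six Phase II participants, after the dose is chosen, and Phase II never opened.

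**It made no difference here.** This largely stands. All participants completed planned ulocuplumab, so early exit did not occur. A reader might infer that the Phase I dose finding is biased, or that someone was counted without having received the combination. The documents do not support that. They say nothing about ibrutinib taken in Cycles 1-2. Section 6 holds ulocuplumab when ibrutinib is held, which makes a long gap in ibrutinib alone less likely, although ulocuplumab schedules may be adjusted after a hold.

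**The cap.** A reader might infer that the limit of 18 blocked replacement. It would bind only if all three levels reached six. Cohort 3 closed at its third participant, so accrual was at most 6 + 6 + 3 = 15.

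**Conclusion.** The concern holds as a minor gap in the design. As written, the 3+3 lets an uninformative participant stand as a full DLT-free place, and the error runs toward passing a level that is too toxic. The size is about 1 to 3 percentage points under an assumed 5-10% loss with midway exit, and up to about 7 with no risk time. It is about 14 to 15 points in a cohort that loses one of its first three at once. These figures rest on assumed DLT and loss rates, and on reduced exposure not raising DLT risk. They are planning figures and do not describe the treated cohorts.

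A reader might also infer that replacement would bring the pass probabilities back exactly to the first row of the table. That is not shown: a sound rule keeps people whose exposure was cut short by toxicity that was not a DLT, and they do not carry the full two-cycle risk.

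**What to change.** For this design or any reuse of it, put a DLT-evaluable set into 5.4, 5.5 and 13.1 in place of treated participants. DLT-evaluable participants are those who:

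- (a) have a DLT in Cycles 1-2; or
- (b) receive a sponsor-set minimum of both drugs in Cycles 1-2 and are observed to the end of Cycle 2; or
- (c) fall short of (b) because of study-drug toxicity.

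Replace any other participant at the same dose level before the escalation decision, and state the 13.2 cap as 18 DLT-evaluable patients. Limb (c) stops replacement from hiding toxicity. The documents give no exposure threshold, so the sponsor must choose one. In doing so it should say how the ulocuplumab delay of up to two weeks that Section 6 allows for plasmapheresis is treated.

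The cost is an occasional extra participant and some delay to escalation. Expected replacements are n × q/(1−q): at an assumed 5% or 10% inevaluable, about 0.5 or 1 on nine evaluable participants, and about 0.95 or 2 on eighteen.

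Enrollment is closed, so the action for the report is limited to one table: DLT counts per dose level with Cycle 1-2 exposure to both drugs. The ibrutinib diaries required by 5.3.2 can supply the ibrutinib part.
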